8.1.4. Immunological correlates of protection

No recognized immunological correlate of protection (CoP) has been established for the antigen used as part of the HRV vaccine. However, an analysis by Cheuvart et al. in 2014 showed that post-vaccination anti-RV IgA seropositivity (Ab concentration ≥ 20 U/mL, measured by ELISA) is a correlate of vaccine efficacy in clinical trials of *Rotarix* [Cheuvart, 2014]. This was confirmed by an independent research group in 2020 [Baker, 2020].

Antibodies against poliovirus types 1, 2 and 3 will be determined by a virus microneutralization test adapted from the WHO Guidelines for WHO/EPI Collaborative Studies on Poliomyelitis [WHO position paper, 1993]. Titers will be expressed in terms of the reciprocal of the dilution resulting in 50% inhibition. The lowest dilution at which serum samples will be tested is 1:8. Antibody titers greater than or equal to 1:8 will be considered as protective.

The immunological assay results will be communicated to the investigator after the end of the study.

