9.3.2. Secondary immunogenicity endpoints analysis

The secondary endpoints are described in Section [3](#).

Anti-RV IgA Ab seroconversion rate and the percentage of participants with anti-RV IgA antibody concentration ≥ 90 U/mL at 1 month post Dose 2 of *Rotarix*; and the percentage of participants with poliovirus types 1, 2 and 3 neutralizing antibody titers $\geq 1:8$ and $\geq 1:64$ at 1 month post Dose 3 of IPV will be summarized by group with 95% CI.

For all antigens and timepoints as applicable, GMT/GMC will be computed with 95% CI. The 95% CI will assume that log transformed titer/concentration is normally distributed. For the purpose of GMT/GMC computation, titer/concentration below the assay cut-off will be assigned half of the cut-off.

For each of the anti-poliovirus types 1, 2 and 3, group GMT ratio at Visit 7 will be computed with 95% CI using an analysis of variance (ANOVA) model on log transformed titer in order to characterize the impact of co-administration on the IPV response. The group GMC ratio, the difference in seroconversion rates and the difference in the percentage of participants with concentration ≥ 90 U/mL will not be computed for anti-RV IgA antibody because a difference may be either attributed to co-administration of *Rotarix* PCV-free with IPV, or to the difference in administration schedule for *Rotarix* PCV-free (Month 0.5 and Month 1.5 in the Co-administration group, and Day 1 and Month 1 in the Staggered group).

Reverse cumulative curve will be provided for each antigen and timepoint as applicable.

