10.2. Appendix 2: Clinical laboratory tests

10.2.1. Protocol required immunogenicity laboratory assessments

Anti-RV IgA antibody determination:

The anti-RV antibody concentrations are determined by a validated anti-RV IgA ELISA. Microtiter plates (96-well) are coated with an anti-RV monoclonal antibody. The wells are washed and incubated with (positive wells) or without (negative wells) RV. Following incubation, the plates are washed and serum, standard and control dilutions are incubated in both types of wells (positive and negative). Bound anti-RV IgA in the wells are detected by incubation with peroxidase conjugated anti-human IgA polyclonal antibodies. Color development proportional to the quantity of bound anti-RV IgA occurs in the presence of a chromogen, TetraMethylBenzidine, and measured spectrophotometrically. Specific optical densities are calculated for each sample/control/standard dilution by measuring the difference between positive and negative wells, the use of negative wells allowing to assess non-specific IgA binding. The concentrations of the samples expressed in units per milliliter are calculated relative to the four-parameter logistic function generated from the standard curve.

Anti-IPV type 1, type 2 and type 3 antibodies determination:

The polio microneutralization assay measures neutralizing antibody titers to poliovirus types 1, 2, and 3 using 96-well microtiter plates. The principle of the test is that the anti-poliovirus antibodies in a serum sample will bind to the virus and block infection of susceptible cells. Because poliovirus is cytopathic, virus that is not bound by antibody infects and lyses cells. The amount of neutralizing antibody is quantitated as a titer based on the last serum dilution to protect susceptible cell culture wells from poliovirus infection and cytopathic effect.

10.3. Appendix 3: AE: definitions and procedures for recording, evaluating, follow-up, and reporting**10.3.1. Definition of an AE**

- An AE is any untoward medical occurrence in a clinical study participant, temporally associated with the use of a study intervention, whether or not considered related to the study intervention.
- Note: an AE can therefore be any unfavorable and unintended sign (including an abnormal laboratory finding), symptom, or disease (new or exacerbated) temporally associated with the use of a study intervention.

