1.1. Objectives, Estimands and Endpoints

Objectives	Endpoints**
Primary (Confirmatory)	

 To demonstrate the immunological non-inferiority of IPV when co-administered with Rotarix PCV-free compared with IPV administered alone. 	
 Anti-poliovirus types 1, 2 and 3 neutralizing Ab seroconversion rate* 1 month post Dose 3 of IPV in the Co-administration and Staggered groups.
Secondary (Descriptive)	

 To evaluate the immunogenicity of IPV when co-administered with Rotarix PCV-free and when administered alone. 	
 Anti-poliovirus types 1, 2 and 3 neutralizing Ab GMTs at 1 month post Dose 3 of IPV in the Co-administration and Staggered groups. Percentage of participants with anti-poliovirus types 1, 2 and 3 neutralizing Ab titers $\geq 1:8$ and $\geq 1:64$ at 1 month post Dose 3 of IPV in the Co-administration and Staggered groups.

 To evaluate the immunogenicity of Rotarix PCV-free when co-administered with IPV and when administered alone. 	
 Anti-RV IgA Ab seroconversion rate** 1 month post Dose 2 in the Co-administration and Staggered groups. Anti-RV IgA Ab GMCs at 1 month post Dose 2 of Rotarix PCV-free in the Co-administration and Staggered groups. Percentage of participants with anti-RV IgA Ab concentrations ≥ 90 U/mL at 1 month post Dose 2 of Rotarix PCV-free in the Co-administration and Staggered groups.

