2. STATISTICAL HYPOTHESES

Primary objective	Null hypothesis

 To demonstrate the immunological non-inferiority of IPV when co-administered with Rotarix PCV-free compared with IPV administered alone. 	
 The difference in seroconversion rate between the Co-administration group and (minus) the Staggered group is below -10% for at least 1 of the anti-poliovirus types 1, 2 and 3 Abs.

Ab: Antibody; IPV: Inactivated poliovirus vaccine; PCV: *Porcine circovirus*

The global type I error will be 2.5%. The primary objective will be achieved if the lower limit of the 2-sided 95% CI for the group difference (Co-administration group minus Staggered group) in seroconversion rate is greater than or equal to -10% for each of the anti-poliovirus types 1, 2 and 3 antibodies.

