4.3.2. Between group assessment

- The asymptotic standardize 95% CI for the difference in the percentage of participants with anti-poliovirus types 1, 2 and 3 neutralizing Ab titers $\geq 1:8$ and $\geq 1:64$ at Visit 7 between Co-administration group minus staggered group will be computed.
- The 95% CI for the ratio of anti-poliovirus type 1, 2 and 3 Ab GMTs at Visit 7 between Co-administration group over staggered group will be computed.

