6.2.9. Immunogenicity data

- In general, the assay cut-off is the value under which there is no quantifiable result available. For an assay with a specific ‘assay cut_off’, the numerical immunogenicity result is derived from a character field (IS.ISSTRES):
 - if ISSTRES is ‘NEG’ or ‘-’ or ‘(-)’, numeric result= assay cut_off/2,
 - if ISSTRES is ‘POS’ or ‘+’ or ‘(+)’, numeric result = assay cut_off,
 - if ISSTRES is ‘< value’ and value<=assay cut_off, numeric result =assay cut_off/2,
 - if ISSTRES is ‘< value’ and value>assay cut_off, numeric result =value,
 - if ISSTRES is ‘> value’ and value<assay cut_off, numeric result =assay cut_off/2,
 - if ISSTRES is ‘> value’ and value>=assay cut_off, numeric result =value,
 - if ISSTRES is ‘<= value’ or ‘>= value’ and value<assay cut_off, numeric result =assay cut_off/2,
 - if ISSTRES is ‘<= value’ or ‘>= value’ and value>=assay cut_off, numeric result =value,
 - if ISSTRES is a value < assay cut_off, numeric result = assay cut_off/2,
 - if ISSTRES is a value >= assay cut_off, numeric result = ISSTRES
 - else numeric result is left blank.

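### SAP 6.2.9 codes a '> value' titre as the bound itself; if any Visit 7 polio titres are reported that way, the GMT ratio is attenuated towards 1, and no censored-data sensitivity analysis is planned

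*SAP*

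**What the plan says.** SAP section 6.2.9 lists how a character assay result becomes a number. The list is generic and applies to any assay with a cut-off. For results known only to exceed a bound it says "if ISSTRES is ‘> value’ and value>=assay cut_off, numeric result =value".

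These numbers feed the polio GMTs. SAP section 4.3.2 plans "The 95% CI for the ratio of anti-poliovirus type 1, 2 and 3 Ab GMTs at Visit 7", Co-administration over Staggered, without naming a model. Protocol section 9.3.2 names it: "group GMT ratio at Visit 7 will be computed with 95% CI using an analysis of variance (ANOVA) model on log transformed titer". It gives the purpose as "in order to characterize the impact of co-administration on the IPV response". Neither document adds a censoring term or a sensitivity analysis for results above a bound.

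On the assay range, protocol section 8.1.4 gives only the lower end: "The lowest dilution at which serum samples will be tested is 1:8". Protocol section 10.2.1 describes a "titer based on the last serum dilution to protect susceptible cell culture wells from poliovirus infection and cytopathic effect". No highest dilution is stated, and nothing says whether high sera are diluted further until an endpoint is found.

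**The concern.** A '> value' result says that the titre is above the bound, not equal to it. Replacing it by the bound lowers the mean log titre. The group with higher titres has more results above the bound and is lowered more, so a true ratio away from 1 is pulled towards 1. The spread is also understated, so the interval is both shifted and too narrow.

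This matters because of what the ratio is for. The planning seroconversion rates are 93.83% to 97.60%, so a moderate drop in titre could leave seroconversion almost unchanged. The GMT ratio is the planned numerical summary of the whole titre distribution. It has no margin and is read as an estimate with an interval, so a shifted estimate and an under-covering interval bear directly on its use.

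**Working it through.** **The plan's own figures.** The plan gives none for the GMT ratio. Its stated power (98.2%, 92.5% and 99.7% by type, 90.4% overall) concerns seroconversion. An exact recalculation of the Miettinen-Nurminen test with 160 per group agrees within 2 points. The coding rule does not enter that calculation.

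**Inputs.**
- From the documents: the coding rule; ANOVA on log titre; 160 evaluable per group; maternal half-life of 28 days.
- Assumed, because the documents are silent: normal log2 titres with SD σ of 1.5 or 2.0; true ratio R of 0.67 or 0.50; a share p of Staggered titres above the top dilution of 5%, 20% or 40%.

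**Formula.** Let U be the log2 top dilution, μ the true mean and a = (U − μ)/σ. The mean after capping is

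m = μΦ(a) − σφ(a) + U[1 − Φ(a)],

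and the reported ratio is 2^(m_Co − m_Stag).

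**Worked case: σ = 1.5, R = 0.67, p = 20%.** Set μ_Stag = 0, so U = 1.5 × 0.842 = 1.262.
- Staggered: m = −1.5 × 0.280 + 1.262 × 0.20 = −0.168. The GMT factor is 2^−0.168 = 0.89, so the GMT is 11% too low.
- Co-administration: μ = log2(0.67) = −0.578 and a = (1.262 + 0.578)/1.5 = 1.227, so 11% are capped. Then m = −0.578 × 0.890 − 1.5 × 0.188 + 1.262 × 0.110 = −0.657.
- Reported ratio: 2^(−0.657 + 0.168) = 2^−0.489 = 0.71.

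**All cases** (ranges run over σ = 1.5 to 2.0):

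| Staggered titres capped | True 0.67 reported as | True 0.50 reported as | Staggered GMT too low by |
|---|---|---|---|
| 5% | 0.68 | 0.51 | 2–3% |
| 20% | 0.71–0.72 | 0.55 | 11–14% |
| 40% | 0.76–0.77 | 0.61–0.62 | 26–33% |

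**Interval.** Simulated trials with 160 per group and a true ratio of 0.67 gave coverage of the nominal 95% interval of about 95% at 5% capped, 91–93% at 20% and 66–76% at 40%. At 40%, the lower limit lies above the true ratio in 24–34% of trials, so the misses are almost all on the reassuring side.

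**Ability to see a lower response.** With a log10 SD of 0.5 and a true ratio of 0.67, the chance that the upper 95% limit falls below 1 is 87% with no capping, 85% at 20% capped and 79% at 50%.

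**Primary endpoint.** At the optimal visit intervals, baseline to Visit 7 is 15 + 30 + 30 + 30 = 105 days (Staggered) or 30 + 30 + 30 = 90 days (Co-administration). The four-fold threshold on the decayed baseline is 4 × 2^(−105/28) = 0.30 × baseline, or 4 × 2^(−90/28) = 0.43 × baseline. Both multiples are below 1. A post-dose titre capped at the top dilution therefore still counts as seroconverted for any baseline at or below the top dilution. Only an infant whose maternal titre exceeds the top dilution could be misclassified.

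**Threshold percentages.** A capped titre is classified correctly at 1:8 and 1:64 as long as the top dilution is at least 1:64.

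**The case against.** The strongest objection is that nothing in the documents shows that a '>' polio result will occur. The line in section 6.2.9 belongs to a general parsing list. If high sera are diluted to endpoint, the bias is zero. This stands: the point is conditional, and none of the capped shares above comes from the plan.

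A reader might infer that the rule hides interference. It does not. The ratio stays below 1, and most of the ability to detect a true 0.67 remains even with half of the Staggered titres capped. A reader might also infer that the GMT ratio is the only planned analysis that could show a reduced response. SAP section 4.3.2 also plans group differences at ≥1:8 and ≥1:64, and section 4.3.1 plans reverse cumulative curves, which show shifts below the cap and would reveal a heavy ceiling. They do not correct the ratio or its interval.

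The consequence is limited too. Polio GMTs are secondary and descriptive, and no group ratio is computed for anti-RV IgA.

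Finally, a censored-normal model is not free of assumptions, because it extrapolates the unseen upper tail. In checks with a true ratio of 0.67 it recovered 0.67 under normality and 0.66–0.67 with heavy tails, but gave 0.62–0.66 with left skew. That is a good reason not to let it replace the ANOVA whenever a single '>' result appears. It does not argue against running it alongside.

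**Conclusion.** The point holds in conditional form. If Visit 7 polio titres are reported as '> value', the coding rule lowers the GMTs and attenuates a true ratio below 1. The effect is negligible at about 5% capped. At 20% it is modest: 0.67 becomes 0.71 to 0.72. At 40% it is material: 0.67 becomes 0.76 to 0.77, with clear under-coverage. These sizes rest on log-normal titres and an assumed log2 SD of 1.5 to 2.0. The actual share cannot be found from the documents. Assuming a log10 SD of 0.5, Staggered GMTs of 256 to 2048 and top dilutions of 1:512 to 1:8192, a true 0.67 could be reported as anything from 0.67 to 0.94, the extreme having 89% of Staggered titres capped.

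The documents do not support reading this as a threat to the confirmatory conclusion. The non-inferiority decision on seroconversion is essentially unaffected. This is a low-cost improvement to a descriptive analysis.

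**What to change.** In SAP sections 6.2.9 and 4.3.2:

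1. Report the number of '>' results at Visit 7 by group and poliovirus type.
2. Keep the protocol's ANOVA on log titre, with the present coding, as the main estimate of the GMT ratio.
3. For any type with '>' results, pre-specify a sensitivity analysis of the GMTs and their ratio by censored-normal maximum likelihood on log titre, right-censored at the reported bound.
4. Leave the coding for seroconversion and the threshold percentages unchanged.

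The cost is one extra model per poliovirus type and a short SAP addition, with no laboratory work and no change to a protocol-defined analysis. If no '>' results occur, nothing is run. The drawback is that the added model relies more heavily than the ANOVA on the log-normal shape of the upper tail, so the two estimates should be shown together.

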6.2.10. Number of decimals displayed

The following decimal description from the decision rules will be used for the demography, immunogenicity and safety/reactogenicity.

Display Table	Parameters	Number of decimal digits
All summaries	% of count, including LL & UL of CI	1
Demographic characteristics	Mean, median, SD	1
Reactogenicity	% of count, including LL & UL of CI	1
Immunogenicity	GMCs/GMTs and Rates (%), including LL & UL of CI	1
Immunogenicity	GMC/GMT ratios, including LL & UL of CI	2
Immunogenicity	Differences between Rates, including LL & UL of CI	2

6.2.11. Trademarks

Trademarks of the GlaxoSmithKline Group of Companies	Trademarks not owned by the GlaxoSmithKline Group of Companies
Rotarix	IPV

